4.3.3 Specimen Processing and Storage

The HCL immunology group will initially begin training NARI lab personnel for specimen collection and storage (if needed). This training can be performed using serone gative volunteer samples, to avoid using more limited seropositive samples. Therefore, sites will be expected to recruit 20 seronegative volunteers at the on-set of the study, and then up to 10 seronegative volunteers for each year of the study.

The negative control samples will be used for:

- Quality controls for freeze/thaw and viability protocols
- HLA screening for population genetics
- Negative controls in immunologic assays

All HPTUs must meet or exceed guidelines that will be outlined in the study-specific procedures manual for cell preparation and preservation quality (Appendix D). While it is clearly optimal to use freshly isolated PBMC for real-time assays, it is likely that in this study, and in future larger HIV-1 prevention and vaccine studies, the use of frozen specimens will be necessary for batch testing. It has been previously shown that cryopreserved PBMC can be used for detection of cellular immune responses in HIV-1 infected volunteers (39;40). NARI will be required to periodically perform quality control analysis of frozen cells by thawing single aliquots of cells from negative controls to assess cell number and viability (detailed in study-specific procedures manual). For example, it would be expected a PBMC recovery 50% or greater of the total number of PBMC stored would be achieved, and that the viability of thawed cells would be approximately 90%. This number is based on previously observed recoveries from cryopreserved PBMC from HIV-1 infected individuals (41;42) Additionally, sites with flow cytometry capacities will be able to do more sophisticated measurements of cell preservation by testing for cell surface marker integrity. It has been previously shown that, cryopreservation of

cells does not significantly alter the cell surface expression of most lymphocyte markers studied (43).

4.3.4 HLA typing

PBMC from HIV-1 uninfected individuals will also be used for HLA typing to be performed in collaboration with [name] Laboratory at The University of New Mexico Health Science Center Albuquerque, New Mexico. NARI would be required to ship a single frozen vial of PBMC to this laboratory for HLA typing. There is increasing evidence that HLA type influences the course of a number of diseases such as HIV-1 and malaria (44;45). Furthermore, identification of CTL epitope specificities using HLA types for modeling binding motifs has become a standard practice in cellular immunology. Therefore, characterizing the HLA types of the population in Pune will be important in understanding risk of HIV-1 infection and the immune response subsequent to infection.

4.3.5 ELISPOT Assays

As mentioned above, NARI will be evaluated for their ability to collect and store blood specimens. Once the laboratory is able to adhere to the quality control requirements outlined above and in the site-specific study manual (Appendix C), they will be encouraged to participate training workshops at Johns Hopkins University as well as on-site and regionalized training. Training will be provided for participation in future virologic and immunologic studies of acute seroconvertors including measurements of T cell function through ELISPOT and flow cytometry analysis (where available). If procedural problems or inconsistencies occur in QC procedures, individual sites will be responsible for internal problem solving, however, communication with the HCL group will be encouraged. Personnel from the HCL will periodically visit the NARI site for technical support and site evaluation.

NARI will identify at lease two key personnel on site as responsible for supervision and implementation of the study protocols. A site PI should be one of the site contacts, and the other should be a key laboratory scientist directly involved in the processing and laboratory testing of specimens. Representatives of the participating site would be invited to join the Protocol Team to contribute to the design of the subsequent immunologic and virologic studies to be undertaken with the specimens in the site repositories. The HPTN Immunology Group will also invite and encourage participation and collaboration with investigators outside of the HPTN for future studies.

Measurement of HIV-1 -specific T lymphocyte responses to HIV-1 infection in exposed, uninfected participants in this protocol will require a highly sensitive assay. There are a number of available assays to be utilized to address the specific research objectives of this protocol, including ELISPOT, tetramer and intracellular cytokine/flow cytometric assays. At this time, the ELISPOT appears to be the assay that could be most efficiently, consistently and reliably initiated in participating HPTU laboratories. However, the HCL will continue to evaluate the available assays and will enlist the expertise of investigators within and without the HPTN and consider utilizing other assays in the future.

The ELISPOT assay is an alternative functional assay that can measure $CD8^+$ T cell function. The read-out of the ELISPOT assay is secretion of IFN- γ from HIV-1 -specific T cells. Secreted IFN- γ is captured onto a membrane-coated ELISA plate by an IFN- γ -specific monoclonal antibody, and developed using standard ELISA reagents. The number of spots counted in a particular sample well corresponds to the number of HIV-1 -specific T cells in the well/total number of cells added. Therefore, the relative frequency of cells that are specific for a particular antigen can be determined. This assay can also measure a positive and negative response for each sample tested. The positive control consists of the addition of PHA to replicates of PBMC samples. A majority of CD3⁺ lymphocytes will secrete IFN- γ in response to this mitogen. The negative controls for this assay are mock-stimulated replicates in which no stimulus is added. This allows for the assessment of background levels of IFN- γ secretion. For purposes of quality assurance, the HCL will create a panel of frozen PBMC to serve as positive and negative control samples. These cells will be sent to the NARI site to test in a blinded fashion in the ELISPOT assay using a standard set of reagents.

An important issue for the ELISPOT assay is the choice of HIV-1 -antigens to use for the *in vitro* stimulation. The use of overlapping pools of HIV-1 gag peptides for *in vitro* stimulation has been shown to be an effective means of characterizing the gag-specific immune response to HIV-1 in acute and chronic infection (46-51). One complicating factor that will need to be addressed is whether to use sequence-specific HIV-1 antigens for the *in vitro* stimulation. Designing peptides that match the predominant HIV-1 strains to which study participants may be exposed at a particular site would be extremely difficult and expensive. Furthermore, because there is limited data on the importance of customizing overlapping peptide sequences to match subtypes of HIV-1 represented at each site, it is not clear that this would outweigh the substantial cost of synthesizing multiple sets of peptides. Therefore, the HCL will attempt to provide reagents that are based on the best information currently available on viral subtype amino acid sequences. These sequences will be obtained from sequencing data from the sites themselves, sequences

published in the current literature, and the compendium of sequence data from the HIV-1 molecular database at the Los Alamos National Laboratory (53).

Based upon the data from prior studies and an initial assessment of the logistical limitations of initiating this type study at multiple HPTU, this proposal will initially focus on measurement of HIV-1 gag-specific ELISPOT responses utilizing a matrix format of pools of overlapping HIV-1 gag peptides(54-57). NARI will initially be provided with a set of HIV-1 subtype C gag peptides. Based upon this initial analysis of the gag-specific responses and upon data from other ongoing studies, we propose to consider expanding this analysis to include assessment of other HIV-1 antigens, including env, pol, nef and tat. The details of the proposed consensus ELISPOT assay with gag peptides are provided in Appendix C. ELISPOT measurements will be made as early and frequently as possible after initial identification of infection. The visit schedule is outlined in Appendix A. The need for these frequent blood draws is comes from data that suggests that the epitope recognition seen in exposed uninfected individuals may be transient and variable.

Based upon the analysis of the ELISPOT data, a decision will be made by a consensus of the protocol team, which includes NARI site investigators and investigators outside of the HPTN, about expanding the analyses to other immunological assays (e.g. tetramer, intracellular flow cytometric assays, co-receptor genetic analysis), other antigens (e.g. nef, pol, env, tat) and other critical scientific questions. New information is continuously being generated that impacts our understanding of events critical to HIV-1 transmission and pathogenesis. To optimize the relevance of this study to the HPTN, the protocol team must include outside expertise and must stay informed about the latest information that might suggest modifications in the specifics of the laboratory assays utilized for this protocol. This protocol must also facilitate and be coordinated with ongoing, related laboratory studies at participating HPTUs, as well as with outside collaborators. The science in this field moves quickly and this laboratory protocol must remain dynamic, flexible, informed and collaborative to optimize this important scientific opportunity.

5.0 Evaluation of Outcomes

5.1 Primary Outcomes

Following the successful implementation of immunologic (ELISPOT) and virologic (viral load measurements) assays at NARI (See quality control and training details above), this project will collect data to address the two stated primary objectives.

5.1.1.Primary Objectives (a).

To determine if the detection of an HIV-1 -specific immune response in exposed uninfected individuals, correlates with risk of subsequent HIV-1 infection.

The initial research hypothesis for this objective, based upon a few prior studies of HIV-1 exposed, uninfected individuals, is that exposed uninfected individuals with CD8mediated recognition of HIV-1 -gag epitopes will demonstrate a lower risk of subsequent HIV-1 infection, compared with exposed individuals that do not recognize HIV-1 gag epitopes. A further hypothesis is that this correlation will be demonstrated in exposed uninfected individuals, who are exposed to recently infected individuals infected with different strains of HIV-1. The primary outcome measures for this analysis will be subsequent HIV-1 infection within the first 2 years of follow-up, and demonstration of an HIV-1 gag-specific response measured in an ELISPOT assay. Based upon this initial analysis of gag-responses and upon data from other ongoing studies, we propose to consider expanding this ELISPOT analysis to include assessment of recognition of other HIV-1 antigens, including env, nef and tat.

5.1.2. Primary Objectives (b).

To determine if immunologic genetic characteristics of exposed uninfected individuals correlates with risk of subsequent HIV-1 infection, across diverse populations.

The initial research hypothesis for this objective, based upon prior studies in a few countries demonstrating that certain HLA class I alleles may be associated with a lower risk of HIV-1 infection, is that there are specific host genetic characteristics that will be associated with a lower risk of HIV-1 infection in exposed individuals from diverse populations infected with different strains of HIV-1. The primary outcome measure for this analysis will be subsequent HIV-1 infection, defined as above, and HLA class I allelic genotype. Based upon this initial analysis of the HIV-1 class I alleles and upon data from other ongoing studies, we propose to consider expanding this analysis to include assessment of HLA Class II alleles and co-receptor genotyping.

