This is a descriptive sub-study proposed for HPTN 034. Therefore, it is not expected that we will have sufficient sample size to definitively address the primary endpoint. Never the less, we will undertake the analysis as outlined on our projected sample size of 20-30 individuals. However, we have also projected that data from this sub-study would also be available for combining with similar data from other HPTN protocols in the future. Our subsequent "meta-analysis" will compare HIV-1 viral set point with the recognition of more than two (>2) gag peptides at any time point within 12 months since estimated time of infection. Separate and similar analyses will be performed for recognition of HIV-1 subtype B gag and non-B gag peptides. Additional analyses will determine if other ELISPOT outcome measures, such as consistent recognition of more than 2 gag peptides at multiple time points, also correlate with viral set point. We predict a 30% difference between the groups with respect to the proportion of individuals who elicit a broad immunologic response (defined above). With a sample size of n=39 per arm from multiple HPTN protocols in the future, we will have 80% power to detect a 30% difference (p=0.05).

Percent ELISPOT response to >2 HIV-1 gag peptides			Estimated Sa	mple Size
<10000 RNA	10000-75000 RNA	>75000 RNA	N per arm	Total N
copies/ml	copies/ml	copies/ml		
70%	50%	30%	93	279
80%	50%	20%	39	117
90%	50%	10%	20	60

Sample Size Estimate

6.3.2 Primary Objective (b).

HLA Class I alleles vs. HIV-1 Viral Set Point.

A similar "meta analysis" of data from 034A and other similar sub-studies is anticipated for this objective. The proportion of individuals with specific HLA Class I alleles will be compared with the viral load set point. Using HLA A2 as an example (known to be associated with a frequently measurable immune response to gag peptides), we posit that a higher percentage of individuals with this allele will fall into the low viral set point category. Again, we will have an 80% power to detect a 30% difference in the proportion of individuals with HLA A2 given a sample size of 39 individuals per arm.

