We, the Principal Investigators, agree to conduct this study in full accordance with the provisions of this protocol. I agree to maintain all study documentation for a minimum of five years from the end of the study, unless directed otherwise by the HPTN Coordinating and Operations Center (CORE). Publication of the results of this study will be governed by HPTN and DAIDS policies. Any presentation, abstract, or manuscript will be made available by the investigators to the HPTN Manuscript Review Committee and DAIDS for review prior to submission.

We have read and understand the information in this protocol and will ensure that all associates, colleagues, and employees assisting in the conduct of the study are informed about the obligations incurred by their contribution to the study.

Name of Principal Investigator		
Signature of Principal Investigator	Date	
Name of Principal Investigator		-
Signature of Principal Investigator	Date	

HPTN 034 B HPTN EXPOSED-UNINFECTED LABORATORY SUB-STUDY **PROTOCOL SUMMARY**

Design:	Laboratory Sub-study for HPTN 034
Study Sites/Population:	Adult men and women who have been identified as HIV-1 uninfected sexual partners of recently HIV-1 infected participants in the HPTN 034A sub-study
Study Duration:	The sub-study is designed to run for the duration of the entire HPTN 034 funding period. Participants will be continuously enrolled and followed for up to two years, as funding allows.
Primary Objectives:	 (a) To determine if the detection of an HIV-1 -specific immune response in exposed uninfected individuals correlates with risk of subsequent HIV-1 infection. (b) To determine if immunologic genetic characteristics of exposed uninfected individuals correlates with risk of subsequent HIV-1 infection.
Primary Endpoints	 (a) HIV-1 antibody seroconversion (b) ELISPOT measurement of HIV-1 peptide-specific T lymphocytes (c) HLA-Class I MHC alleles
Secondary Objectives:	 (a)To determine if the detection of an HIV-1 -specific immune response in exposed-uninfected individuals correlates with the HIV-1 viral set point in individuals that subsequently become HIV-1 infected. (b) To compare the epitope specificity of the HIV-1-specific immune response of exposed-uninfected individuals with that of their recently infected partners. (c) To assess the feasibility of establishing a prospective cohort of recently infected individuals and their primary sexual partners for participation in HPTN HIV-1 prevention trials of discordant couples.

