6.3 Statistical Considerations and Sample Size Calculations

Based upon assumptions outlined below for each of the two primary objectives, the target samples size for this study is a minimum of 20 subjects who are HIV-1 -exposed uninfected individuals with recently infected partners. For both primary objectives, frequency of HIV-1 infection will be an outcome measure. Patients will be divided into an infected and uninfected

cohort and compared with respect to the presence or absence of any prior detectable immune response as measured by Elispot.

6.3.1 Primary Objectives (a). Gag-specific ELISPOT Response vs. subsequent HIV-1 Infection.

For the purposes of comparing ELISPOT response to incidence of infections, gag-specific ELISPOT responses will be scored as positive or negative. As outlined in Appendix C, all experiments will be performed in duplicate wells. The IFN- γ -expressing spots will be calculated as the number of spots per 10⁵ stimulated PBMCs. Results will be expressed as net peptide-specific IFN- γ spots / 10⁵ PBMC. A positive peptide-specific response (responders) will be defined as a mean of greater than 5 spots above the mean spots of the mock-stimulated PBMC. Study participants will be expected to have multiple ELISPOT assays within the first 12 months of follow-up (See Appendix A). For the purpose of the sample size calculation, our initial analysis will compare HIV-infection with a positive response to any gag peptide, at any time point within 12 months since enrollment. Separate and similar analyses will be performed for recognition of HIV-1 subtype B gag and non-B gag peptides. Assuming a 20% seroconversion rate among the exposed uninfected cohort resulting in 20 acutely infected patients, we would have 80% power to detect at least a 25% difference in the proportion of individuals who elicit a gag immune response between the two groups (infected and uninfected).

Difference in proportion of patients with	Total sample size (unequal arms assuming
gag response	20% seroconversion rate)
20%	238
25%	138
30%	86

6.3.2 Correlation of HLA allelic expression with risk of subsequent infection.

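### 034B's two-year infection outcome is analysed as a plain infected/uninfected split although follow-up will be unequal, and the 20% seroconversion assumption has no stated period

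*Supplement*

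**What the plan says.** 034B section 5.1.1 sets the outcome for the ELISPOT objective: "The primary outcome measures for this analysis will be subsequent HIV-1 infection within the first 2 years of follow-up". Section 5.1.2 uses the same outcome for the HLA objective.

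The 034B Protocol Summary (Study Duration) says "The sub-study is designed to run for the duration of the entire HPTN 034 funding period" and "Participants will be continuously enrolled and followed for up to two years, as funding allows". Entry is therefore staggered, and the end of follow-up depends on funding.

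Section 6.3 gives the comparison: "Patients will be divided into an infected and uninfected" cohort, contrasted on whether any prior ELISPOT response was detected. Section 6.3.1 adds that "gag-specific ELISPOT responses will be scored as positive or negative", counting a response to any gag peptide at any time in the 12 months after enrolment. Section 6.3.2 compares HLA alleles between the same two groups.

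On size, section 6.3.1 starts from this premise: "Assuming a 20% seroconversion rate among the exposed uninfected cohort resulting in 20 acutely infected patients". On that basis it claims 80% power for a gap of 25 points or more in gag response. Its table gives totals of 238, 138 and 86 for differences of 20, 25 and 30 points. No period is attached to the 20%.

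034B contains no minimum follow-up for being classed as uninfected, no censoring rule, no person-time and no retention figure. The companion 034A (section 6.3) does set a floor of at least one year retained.

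**The concern.** The objective concerns risk of later infection over two years. A two-way split estimates that risk only if everyone is observed for two years or until infection. The plan itself provides for unequal observation, through continuous entry and a funding-dependent end.

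Two things follow. First, a participant seen for three months without seroconverting has only the uninfected group to fall into, so that group mixes people followed for two years with people hardly observed. Some will be infected later, unseen. This dilutes both the ELISPOT and the HLA contrasts.

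Second, ELISPOT status builds up during follow-up. 034B Appendix A stores cells at months 0, 3, 6, 9 and 12. A participant infected at month 4 has two samples from before infection; one who stays uninfected through month 12 has five. That favours a protective-looking result. Early losses placed in the uninfected group also have few samples, which pushes the other way. The net direction is unknown and the plan does not control it.

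The number of infections, which drives power, also depends on time observed, and the 20% is given without a period.

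**Working it through.** **Step 1. Reproduce the plan's table.** 034B states neither the background response nor alpha. I take two-sided 0.05 (034A section 6.3.1 uses p=0.05), 80% power, and four uninfected per infected participant. The background is inferred: 60% response in the infected against 80%, 85% or 90% in the uninfected (40% against 20%, 15% or 10% gives the same).

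n(infected) = [1.96·√(1.25·p̄(1−p̄)) + 0.842·√(p₁q₁ + p₂q₂/4)]² / (p₁−p₂)², with p̄ = (p₁+4p₂)/5 and total = 5n.

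For 60% against 85%: p̄ = 0.80; (1.96×0.4472 + 0.842×0.5214)² / 0.0625 = 27.7; total 138. The 20- and 30-point rows give 238 and 85, against the stated 238 and 86. The table reproduces under this one background.

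**Step 2. Put a period on the 20%.** If it is a full two-year risk, the hazard is h = −ln(0.8)/2 = 0.1116 per year. The main protocol (section 5.3.1) expects 11.8/100PY in uninfected partners. That gives 1−exp(−0.236) = 21.0% over two years but 1−exp(−0.118) = 11.1% over one. At that rate, 20% needs nearly complete two-year follow-up.

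**Step 3. Share seen to seroconvert under incomplete follow-up.** With constant loss hazard l: observed share = h/(h+l) × [1−exp(−2(h+l))].

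- 94% retained at 24 months (33 of 35 in the site's acute-infection cohort, main protocol section 1.3): l = 0.0294; 0.7913 × 0.2457 = 19.4%.
- 90% semiannual (main protocol section 5.3.1), so 0.9⁴ = 66% at 24 months: l = 0.2107; 0.3462 × 0.4751 = 16.4%.
- 81% semiannual (the site's recent cohort, same section), so 0.81⁴ = 43% at 24 months: l = 0.4214; 0.2093 × 0.6556 = 13.7%.
- Worst case, follow-up uniform over 0 to 24 months with no other loss: 1 − (1−0.8)/(2×0.1116) = 10.4%.

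**Step 4. Consequences**, at total N = 138 and 60% against 85%:

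| Scenario | Observed infected share | Infected at N=138 | Power | Total N for 80% power |
|---|---|---|---|---|
| Complete two years | 20.0% | 27.6 | 79.9% | 138 |
| 94% at 24 months | 19.4% | 26.8 | 79% | 141 |
| 90% semiannual | 16.4% | 22.7 | 75% | 158 |
| 81% semiannual | 13.7% | 18.9 | 70% | 181 |
| Uniform 0–24 months | 10.4% | 14.3 | 62% | 227 |

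The power column reflects only the smaller infected group, not the dilution in step 5.

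**Step 5. Dilution.** Share of the default uninfected group infected later within two years = (20% − observed)/(1 − observed): 0.7%, 4.3%, 7.3% and 10.7%. If loss is unrelated to response, a true 25-point contrast shrinks to about 24.8, 23.9, 23.2 and 22.3 points.

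**Step 6. What would still deliver 20%.** A hazard of 13.9/100PY with 90% semiannual retention, or 23.2/100PY with uniform 0–24 months of follow-up.

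**The case against.** A reader might infer that 034B instructs that lost or late-entering participants be counted as uninfected. It does not. That is what the two-way split does by default; the text is silent, and excluding them would fit it equally well.

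A reader might also infer that the 20% will not be reached. The documents do not support that either. The 20% has no time base and may already mean observed seroconversions. Section 4.1 of 034B describes acutely infected people as especially infectious, so their partners may have a rate above 11.8/100PY. The closest 24-month retention precedent, 94%, leaves almost no shortfall, although it comes from infected people rather than partners. The 10.4% case assumes that all follow-up stops when a two-year enrolment closes. No text says so, and Appendix A schedules visits to month 36. The dilution itself is modest.

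It is also fair that loss handling is commonly left to an analysis plan, and none is shown. That answers a complaint about missing detail. It does not answer this point: section 6.3 names a method, and that method does not estimate the risk named in section 5.1 when follow-up is unequal.

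Finally, the stated minimum of 20 participants yields about 4 infections at 20%, too few for any method to be informative. That is a separate size problem. It limits the practical effect within 034B but does not make the split suitable.

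**Conclusion.** The point holds as a mismatch between outcome and analysis. A two-year outcome, staggered and funding-dependent follow-up, and a plain split do not fit together, and ELISPOT status shares the dependence on time observed. Dilution is about 0.2 to 2.7 points of a 25-point contrast across the scenarios. The bias from unequal numbers of assays is not quantified, and its direction is not fixed by the text.

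The 20% is at risk, not refuted. Read as a full two-year risk, it becomes 19.4% to 13.7% observed under the three retention figures found elsewhere in the documents, and 10.4% in the worst case. Power at N = 138 is then about 79% to 70%, and 62% in the worst case. These figures rest on a constant hazard, loss unrelated to infection or response, an inferred 60% against 85% response, two-sided 0.05, and retention borrowed from other cohorts because 034B gives none.

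**What to change.** In 034B section 6.3, replace the infected/uninfected comparison with time to seroconversion, or infections per person-year, censored at the last HIV test. The main protocol already uses seroconversions per person-year for its own incidence objective (sections 5.3.1 and 5.4).

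Compare by HLA as a baseline factor. Treat ELISPOT as a time-dependent covariate, or classify it at a landmark such as the enrolment assay and count infections from then on. Comparing rates by any positive response in 12 months would credit responders with guaranteed infection-free time (immortal-time bias) and favour the protective hypothesis.

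State the follow-up period to which the 20% applies, and restate the expected number infected with an allowance for incomplete follow-up.

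The cost is slightly more analysis work and a less favourable stated power. No new data are needed: 034B Appendix A already schedules an HIV test at every quarterly visit and stores cells from enrolment onward.
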